The imbalance in the microbial equilibrium is termed “dysbiosis”, which has been further defined as a disturbance to gut microbiota homeostasis due to an imbalance in the bacteria itself, changes in their functional composition and metabolic activities. Dysbiosis has been implicated in a wide range of diseases including irritable bowel syndrome (IBS) (**DeGruttola et al.,2016**).

Gut dysbiosis, plays a fundamental role in the pathogenesis of IBS. It was found in IBS patients that gastrointestinal dysbiosis associated with visceral

hypersensitivity, increased gut permeability, mucosal immune activation, chronic inflammation, chronic fatigue, anxiety, and depression (**Wang et al.,2020**).

Irritable bowel syndrome (IBS) is a common functional gastrointestinal disorder, with signs and symptoms including cramping, abdominal pain, bloating, gas, and diarrhea or constipation, or both (**Gupta and Maity, 2021**).

Patients with IBS have shown success with dietary interventions; specifically limiting short-chain carbohydrates known as fermentable oligosaccharides, disaccharides, monosaccharides and polyols (FODMAP). These carbohydrates have shown to be slowly absorbed and highly fermentable, which contributes to the gastrointestinal symptoms. Restriction of FODMAPs has been shown to improve symptoms in 70% of patients with IBS. Diet modifications and exercise combined showed a significant positive improvement in irritable bowel syndrome. (**Sharaf et al.,2021**).

Exercise is a well-established way to alleviate constipation, distension and also for maintaining proper bowel function and reducing stresses. Physical activity improves colonic transit time, gas transit, and bloating by stimulating gastrointestinal motility and most importantly it is becoming more accepted as a safer and effective treatment for irritable bowel syndrome (**Song et al.,2018**).

Exercise can determine changes in the gut microbial composition playing a positive role in energy homeostasis and regulation. Low intensity exercise can influence the gastrointestinal tract reducing the transient stool time and thus the contact time between the pathogens and the gastrointestinal mucus layer . As a consequence, it seems that exercise has protective effects, reducing the risk of colon cancer and inflammatory bowel disease (**Monda et al.,2017**).

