Subjects will be delimited to patients with irritable bowel syndrome selected from the outpatient of national nutrition institute with the following criteria:

- Sixty six patients with irritable bowel syndrome of both genders.
- Their ages ranged from 20 to 45 years.
- Their Body mass index ranged from 30 to 34.9.
- Patients will be divided into 3 groups
 - **Group A:** Patients will receive moderate intensity continues training exercise program along with following Low fermentable, oligosaccharides, disaccharides, monosaccharides and polysaccharides diet plan (FODMAPs diet).
 - **Group B:** Patient will receive high intensity interval training exercise program along with following FODMAP diet plan.

- **Group C:** Patients will follow FODMAP diet plan only.
- Patients will be excluded if:
 - - Uncontrolled hypertension
 - - Gastrointestinal bleeding
 - - Colorectal cancer or any terminal diseases
 - - Communication disorders

Basic Assumptions:

It will be assumed that:

- 1) The primary medical assessment will be done to every participating patient who includes:
- 2) Complete medical history (personal, present and past)
- 3) All patients will stick to the program and will follow instructions.
- 4) All other factors which may influence the outcome such as noise and distraction will be controlled.

Hypothesis:

It will be hypothesized that there will be no significant difference between the moderate continuous versus high interval intensity training on gut dysbiosis and glucagon like peptide hormone in irritable bowel syndrome.

CHAPTER II

REVIEW OF LITERATURE

The human gastrointestinal (GI) tract represents one of the largest organ between the host, environmental factors and antigens in the human body. In an average life time, around 60 tonnes of food pass through the human GI tract, along with an abundance of microorganisms from the environment which impose a huge threat on gut integrity. The collection of bacteria, archaea and eukarya colonising the GI tract is termed the ‘gut microbiota’ and has co-evolved with the host over thousands of years to form an intricate and mutually beneficial relationship (**Thursby and Juge,2017**).

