The gut microbiota enjoys a mutualistic relationship with the host, harvesting additional energy and nutrients from the diet and protecting the host from pathogens. The resident bacteria produce a wide range of metabolites and chemicals that influence host function and these include short-chain fatty acids such as butyrate, which is essential for the integrity of the colonic epithelium. However, there is potential for these mechanisms to be disrupted as a result of an altered microbial composition, known as dysbiosis (**Lin and Zhang,2017**).

Human Gut dysbiosis is linked to many pathologic conditions disturbing the energy metabolism; such as obesity and atherosclerosis. The microbiota in the human gut is mostly composed of bacterial phyla: Firmicutes and Bacteroidetes (**Thursby and Juge,2017**).

Firmicutes bacteria are Gram-positive one. It plays a key role in the nutrition and metabolism of the host through SCFA synthesis. Through their metabolic products, Firmicutes bacteria are indirectly connected with other tissues and organs and regulate hunger and satiety. In contrast, Bacteroidetes bacteria are Gram negative and associated with immunomodulation. Increased or decreased

Firmicutes / Bacteroidetes (F/B) ratio are associated with the development of obesity or irritable bowel disease (IBD) (**Stojanov et al.,2020**).

Short-chain fatty acids (SCFAs), the primary metabolite for colonocytes, are produced in the intestinal lumen by commensal anaerobic bacteria via carbohydrate fermentation. They play a role in preserving gut barrier functions, and have immunomodulatory and anti-inflammatory properties also it regulates the synthesis of the hunger-suppressing hormones leptin, peptide YY, and glucagon-like peptide 1. The gut microbiota can also affect appetite and satiety via vagus nerve activation or immune-neuroendocrine mechanisms (**Protincasa et al.,2022**).

Irritable bowel syndrome (IBS) is a common gastrointestinal disorder characterized by chronic abdominal pain and changes in bowel habits without any known organic causes (**Aziz and Simern, 2021**).

Fecal SCFAs abnormalities have been reported in patients with IBS, implying that alterations in SCFAs might be related to IBS. The cause of IBS remains unknown, and no single treatment is found to be universally applicable to all patients with IBS (**Sun et al., 2019**).

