Among humans, positive correlations were reported between bacterial diversity, butyrate-producing bacteria and cardiorespiratory fitness (VO₂max), and higher turnover of carbohydrates and proteins, and concentrations of short-chain fatty acids in athletes compared to sedentary controls. There is also growing evidence that physical activity status and exercise training may shape the gut microbiome (**Cataldi et al.,2022**).

Physical activity stimulates bacterial community richness by altering SCFAs-producing species, as well as favoring the colonization of health and athletic performance-promoting strains. The ability to promote a bacterial

composition capable of protecting the intestinal mucosa also it was found that the effects on gut microbiome seem to gradually disappear when the physical activity is no longer practiced (**Cataldi et al., 2022**).

Moderate aerobic exercise affects the intestinal system mainly through gut immune function gut barrier integrity through tight junction proteins expression and IgA production hypothalamic–pituitary–adrenal (HPA) axis stimulation which, in turn, affects enteric nervous system and intestinal transit time, as well as gut motility, intestinal pH and gut hormones release and bile acids metabolism within enterohepatic circulation (**Cella et al.,2021**).

High intensity interval training (HIIT) encompasses exercise prescriptions that are tailored to individual needs and can be used in most any exercise setting. This ability to adapt makes HIIT a valuable tool in the exercise programming of patients with a chronic disease. HIIT has a positive effect on the Bacteroidetes/Firmicutes ratio and also increased the alpha diversity in gut microbiota (**Denou et al.,2016**).

Chapter III

[figure not shown]
PATIENTS, MATERIALS AND METHODS

The current study is designed to compare between the effect of moderate continuous and high interval intensity training on gut dysbiosis and glucagon like peptide hormone in irritable bowel syndrome.

I. Patients:

This study will be carried out on sixty six irritable bowel syndrome patients of both sexes with an age range between twenty to forty five years. Patients will be recruited and practical work of the study will be carried out in national nutrition institute physiotherapy out clinic. Patient will be randomly assigned to three groups.

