To avoid type II error, sample size calculation is performed using G*POWER statistical software (version 3.1.9.2; Franz Faul, Universitat Kiel, Germany). To detect a large effect size of 0.4 with power of 80% and $\alpha=0.05$, the required sample size required for this study was $N=66$.

Ethical consideration:

- Approval of faculty ethical committee.
- The study procedure will be explained for all participants.
- Confidentiality will be assured.
- An informed consent will be taken from each subject prior to participation.

(Appendix I)

Criteria for the patient selection:

Inclusion criteria:

- 1) Patients will be selected with age range of 20 to 45 years of both genders.
- 2) Body mass index (BMI) will range from 30 to 34.9 kg\m².
- 3) Having more than one symptom for ROME IV for IBS diagnostic criteria **(Appendix II).**
- 4) Prediabetic with glycated hemoglobin HbA1c of 5.7 – 6.4.
- 5) Sedentary subjects with daily steps count less than five thousand steps measured by pedometer **(Prince et al.,2020).**

Exclusion criteria:

Patients with the following criteria will be excluded from the study:

- 1) Communication disorders
- 2) Gasterointestinal bleeding
- 3) Antibiotics or probiotics in the last 2 months
- 4) Recent surgeries in the last 6 months
- 5) Colorectal cancer or any terminal diseases
- 6) Fibromylgia or Multiple sclerosis
- 7) Palpable abdominal mass
- 8) Cardiovascular diseases

- 9) Active smokers
- 10) Musculoskeletal injuries that interfere with exercise program
- 11) Upper respiratory infections
- 12) Uncontrolled hypertension

Patients will be divided into 3 groups:

- **Group (A):** This group will include 22 patients with IBS. These patients will receive 40 minutes of MICT on the treadmill: 5 minutes of warm-up followed by 30 minutes of 65-75% of target heart rate ending with a 5 min cool-down period for 12 weeks along with following low FODMAP diet plan.
- **Group (B):** This group will include 22 patients with IBS. These patients will receive HIIT sessions consisting of a 30 minutes treadmill session a 5 minutes warm-up followed by 10 bouts of 1 minute at 90% of target heart rate interspersed by 10 bouts of 1 min of active recovery at 50% of target heart rate (totaling 20 min), and a 5 minutes cool-down period for 12 weeks along with following low FODMAP diet plan.
- **Group (C)** This group will include 22 patients with IBS. These patients will follow low FODMAP diet plan for 12 weeks

Materials and Methods

- **Evaluation**

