Out comes to be measured:

1) Primary outcomes

- a- Short chain fatty acids via gas chromatography
- b- Glucagon like peptide 1 via Elisa kit

2) Secondary outcomes

- a- Irritable bowel syndrome scoring system

- b- Irritable bowel syndrome quality of life questionnaire (IBS QoL)
- c- Change in body weight via body mass index (BMI)

Evaluation equipment and tools:

a) Gas chromatography: SCFAs butyrate and acetate

For SCFA analyses, fecal sample will be separated. Applying four analytes, including total SCFAs, acetate, propionate, and butyrate, will be targeted. Final concentrations will be calculated based on internal standards and are expressed as micromoles per gram of wet feces ($\mu\text{mol/g}$). Techniques and predictive approaches will be used across. gas chromatography will be used to quantify Short Chain Fatty Acids (SCFAs) from fecal samples (**Chen et al.,2021**).

b) Elisa Kit for serum GLP 1 hormone

This kit is an Enzyme-Linked Immunosorbent Assay (ELISA). The plate will be pre-coated with Human GLP-1 antibody (**Kuhre et al.,2015**).

c) Weight and Height measurements

Weight and height will be recorded to calculate body mass index (BMI) according to the following equation: (**Shukohifar et al.,2022**)

$$\text{BMI} = \text{weight}/\text{height}^2 \text{ (Kg/m}^2\text{)}.$$

d) IBS severity scoring system (Appendix III)

This five-item questionnaire will measure IBS symptom severity by addressing abdominal pain (frequency and severity), bloating, dissatisfaction with bowel habits, and interference with daily activities. Each question score ranges from 0 to 100 and a higher score indicates more severe GI symptoms. A total score of 75–175 represents mild IBS, 176–300 moderate IBS and >300 severe IBS (**Zeid et al.,2020**).

e) Irritable bowel syndrome quality of life questionnaire (IBS QoL) (Appendix IV)

The IBS-QoL is a condition-specific instrument will be used to assess the impact of IBS and effects of treatment. It consists of 34 questions which cover eight domains including dysphoria, interference with activity, body image, health worry, food avoidance, social reaction, sexual, and relationships. Each item has a five-point response scale (not at all, slightly, moderately, quite a bit, extremely). The responses are summed and averaged for a total score and transformed to a scale between 0 and 100: higher scores indicating better IBS-specific QoL (Hou et al.,2015).

3-Management procedure:

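### The entry rule on gut-active exposures stops at antibiotics and probiotics; fermentable fibre or prebiotic supplements and an existing low-FODMAP diet are neither restricted nor specified to be recorded, although they act on the substrate of the primary SCFA outcome

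*Combined protocol and SAP*

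**What the plan says.** Chapter III, Exclusion criteria, item 3 excludes "Antibiotics or probiotics in the last 2 months". None of the other eleven exclusions or five inclusion criteria, nor the shorter list under Delimitations, mentions fibre or prebiotic products, laxatives, other IBS medicines or diet before entry. The outcomes, tools and management procedure include no diet history, food diary, dietary adherence measure or log of concomitant products.

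The primary outcomes are "Short chain fatty acids via gas chromatography" and "Glucagon like peptide 1 via Elisa kit". Chapter II says that SCFAs "are produced in the intestinal lumen by commensal anaerobic bacteria via carbohydrate fermentation" and that they help regulate GLP-1. All three groups follow a low-FODMAP diet for 12 weeks, and Groups A and B add exercise. SCFA is expressed per gram of wet faeces. The introduction says that low-intensity exercise acts on the gut by "reducing the transient stool time and thus the contact time between the pathogens and the gastrointestinal mucus layer".

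On setting, the plan says "Patients will be recruited and practical work of the study will be carried out in national nutrition institute physiotherapy out clinic". Basic Assumptions lists a general medical history and states "All other factors which may influence the outcome such as noise and distraction will be controlled". The data analysis section lists means, standard deviations and Pearson correlation. It gives no between-group model and no covariate.

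**The concern.** On the plan's own account, SCFA output depends on the bacteria and on the carbohydrate that they ferment. Item 3 deals with exposures that change the bacteria. Nothing deals with exposures that change the substrate before entry, although the plan treats substrate as active enough to be the common treatment in every arm.

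Three things are at stake. First, users and non-users mixed within an arm widen the spread of SCFA, and with 22 per arm their numbers can differ by chance. Second, a patient who already follows the diet has less diet-related change left to show. Third, patients know whether they exercise, and the plan describes no masking. If symptoms change differently by arm, patients may start or stop such products differently by arm, and no planned data item would show it.

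The last point cannot be repaired at analysis, because the data would not exist.

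**Working it through.** **1. The plan's own figure.** Inputs from the sample size paragraph: effect size 0.4 (read as Cohen's f for a three-group one-way ANOVA), α = 0.05, power 80%, N = 66. The noncentrality is N·f² = 66 × 0.16 = 10.56, which gives power 0.818. N = 63 gives 0.798. The smallest balanced N is therefore 66 and the plan's figure reproduces. The sample size is not in dispute, but it has little reserve.

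**2. What is covered.**

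| Exposure | Restricted at entry | Named as a data item | Link to SCFA in the documents |
|---|---|---|---|
| Antibiotics, probiotics | Yes, 2 months | No | Bacteria |
| Fermentable fibre, prebiotic supplements | No | No | Fermentation substrate |
| Low-FODMAP diet already in use | No | No | Fermentation substrate; same as the trial diet |
| Laxatives, other bowel-active medicines | No | No | Indirect: transit time, wet-faeces unit |

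**3. Effect on precision (illustration).** The documents give neither the share of users nor the size of the shift, so both are assumed. Let the SD without users be 1, the share of users q, and the SCFA shift in users e. The SD becomes √(1 + q(1−q)e²). The reference is the two-arm difference detectable with 80% power at 22 versus 22, two-sided α = 0.05. That is 0.8646 SD, calculated here and not stated in the plan.

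| e | q | Added variance | SD factor | Two-arm power | Three-group power (f = 0.4 ÷ SD factor, N = 66) |
|---|---|---|---|---|---|
| 0 | – | 0 | 1 | 80.0% | 81.8% |
| 0.5 | 10% | 0.0225 | 1.011 | 79.1% | 80.9% |
| 0.5 | 20% | 0.0400 | 1.020 | 78.4% | 80.2% |
| 0.5 | 30% | 0.0525 | 1.026 | 78.0% | 79.7% |
| 1 | 10% | 0.09 | 1.044 | 76.5% | 78.2% |
| 1 | 20% | 0.16 | 1.077 | 73.9% | 75.5% |
| 1 | 30% | 0.21 | 1.100 | 72.1% | 73.6% |

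**4. Chance imbalance.** With independent binomial counts in arms of 22, the chance that two given arms differ by at least 5 users (5/22 = 23 percentage points) is 2%, 9% and 14% at q = 10%, 20% and 30%. For any two of the three arms it is 6%, 20% and 30%. This is not a loss on top of step 3. At q = 10% and e = 1, the standard error of an arm difference is √(2/22) = 0.302 without users. The imbalance contributes √(2 × 0.09/22) = 0.090, and √(0.302² + 0.090²) = 0.315 = 0.302 × 1.044, the inflated standard error already used.

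**5. Bias between arms.** Assume that SCFA is measured before and after the 12 weeks and that effects add. Let D be the diet effect in a patient new to the diet and E the exercise effect. If a share q already follows the diet and so shows no further diet change, the expected change is (1−q)D + E in an exercise arm and (1−q)D in Group C. The difference is E, whatever q is. Change from baseline is diluted in every arm; the contrast between arms is not shifted.

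**The case against.** The strongest case on the other side is that randomisation and a common diet already protect what the trial sets out to compare, moderate continuous against high-intensity interval training. That stands. A reader might infer that prior dieters spoil Group C as a reference. The documents do not support this: such patients are expected equally in all arms, and step 5 shows that the term cancels.

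The power loss is also easy to overstate. It depends on an assumed shift; at 0.5 SD it is 1 to 2 percentage points. It is measured from a hypothetical SD without users, whereas the plan powers on a standardised effect and gives no SD. A stable shift largely cancels in change from baseline, and adjustment for baseline SCFA would absorb much of it. All of this stands.

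A reader might also infer that these exposures go wholly unrecorded, or that laxatives drive SCFA directly. A general medical history could pick up some use, so the supportable statement is that recording is not specified. The fermentation mechanism covers fibre, prebiotics and diet; for laxatives the documents offer only transit time and the wet-faeces unit. That patients at a nutrition institute already follow the diet is plausible but not documented.

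The on-study diet limits fermentable intake equally in all arms, but it does not name supplements. The statement that other factors will be controlled is an assumption with no procedure behind it, and its examples are noise and distraction. Neither answers the missing record.

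**Conclusion.** The point holds as a gap in scope and recording. Item 3 limits exposures that act on the bacteria and leaves out those that act on the substrate, and none of them is a specified data item. The consequences are lost precision, chance imbalance at 22 per arm, diluted diet-related change in every arm, and on-study changes in use that could differ by arm without being seen. Bias in the between-arm comparison from pre-entry use is not among them.

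The size is unknown. Over the assumed 10% to 30% of users, two-arm power falls from 80% to 79.1%–78.0% for a 0.5 SD shift and to 76.5%–72.1% for a 1 SD shift. An analysis adjusted for baseline SCFA would lose less if use is stable. The change is worth making because it is cheap and the information cannot be recovered later; the gap does not invalidate the trial.

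**What to change.** - **Eligibility.** Extend item 3 to fermentable fibre or prebiotic supplements and to a low-FODMAP diet already in use. The investigators should set the look-back window; the documents give no basis for a particular length.
- **Recording.** Record these exposures, laxatives and other IBS medicines at baseline and week 12 in all three arms, and report them by arm. An eligibility line cannot reveal use that starts or stops after randomisation; the week 12 record can.
- **Analysis.** Specify a between-group analysis of SCFA adjusted for baseline SCFA, with a sensitivity analysis that adds baseline use. The data analysis section currently has no between-group comparison to which such an adjustment could attach.

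**Cost.** One line in eligibility and one medication-and-diet field on two forms. Recruitment would be slightly slower in a population already narrowed to IBS, BMI 30 to 34.9, prediabetes and fewer than 5,000 steps a day. If the wider exclusion is judged too costly, recording alone still keeps most of the benefit.

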After collecting the consent forms, will be examined by the researcher for the inclusion and exclusion criteria. Each eligible patient (according to the consent form and examination) will participate in the study.

Group A

Patients will receive moderate intensity continuous training (MICT).

The program will be in form of: (Clark et al.,2020).

- **Frequency:** Moderate continues training will be scheduled 3 times per week for 12 weeks
- **Intensity:** 65-75% of target heart rate.
- **Duration:** 40 minutes per session. Patients will be instructed to follow low fermentable short chain carbohydrates diet (low FODMAP) intervention for 12 weeks limiting daily fermented carbohydrate and dairy products intake and increase intake of protein, whole grains, fruits and vegetables

(Appendix V)

- **Group B**

Patients will receive high intensity interval training (HIIT)

The program will be in form of: **(Clark et al.,2020).**

- **Frequency:** High intensity interval training will be scheduled 3 times per week for 12 weeks
- **Intensity:** 90% of target heart rate including 10 bouts of 1 minute interspersed with 10 bouts of 1 minute of active recovery 50% of target heart rate.
- **Duration:** the session will last 30 minutes includes warming up and cooling down periods

Patients will be instructed to follow low fermentable short chain carbohydrates diet (low FODMAP) intervention for 12 weeks limiting daily fermented carbohydrate and dairy products and increase intake of protein, whole grains, fruits and vegetables

Group C

Patients will be instructed to follow low fermentable short chain carbohydrates diet (low FODMAP) intervention for 12 weeks limiting daily fermented carbohydrate and dairy products and increase intake of protein, whole grains, fruits and vegetables **(Vareny et al.,2017).**

Only the patients who will attend > 80% of the exercise training sessions will be included in this study.

Data Analysis and statistical design

- The collected data was analyzed using the statistical program SPSS ver. 20.0.
- The mean and standard deviation were calculated for all measured variables.
- Pearson correlation coefficient was used to determine the relationship between the measured variables.
- Statistical significance was set at $p < 0.05$.

REFERENCES

Aziz I & Simrén M (2021). The overlap between irritable bowel syndrome and organic gastrointestinal diseases. *The Lancet Gastroenterology & Hepatology*, 6(2), 139–148.

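### The SCFA primary outcome is not fixed to one analyte and no rule links it to GLP-1, so the stated 0.05 and 80% hold together only under conditions the plan does not set

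*Combined protocol and SAP*

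**What the plan says.** All references are to the combined protocol and SAP.

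- **Primary outcomes (list of outcomes, Chapter III).** There are two: "Short chain fatty acids via gas chromatography" and "Glucagon like peptide 1 via Elisa kit". The list names no acid.
- **Evaluation equipment and tools, item a).** The heading reads "Gas chromatography: SCFAs butyrate and acetate". The text under it reads "Applying four analytes, including total SCFAs, acetate, propionate, and butyrate, will be targeted". A unit is given ("Final concentrations will be calculated based on internal standards and are expressed as micromoles per gram of wet feces"), but no analyte is marked as primary.
- **Patients, sample size paragraph (Chapter III).** One calculation is given: "To detect a large effect size of 0.4 with power of 80" per cent and α = 0.05, leading to N = 66. It names no test, outcome or effect-size metric. The groups are 22 each.
- **Hypothesis (Chapter I).** A single sentence covers both outcomes: "there will be no significant difference between the moderate continuous versus high interval intensity training on gut dysbiosis and glucagon like peptide hormone". It does not say what follows if the two disagree.
- **Data Analysis and statistical design.** Means, standard deviations and a Pearson correlation are listed, then "Statistical significance was set at" p < 0.05. No testing order, multiplicity method or success rule is given.

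**The concern.** Two choices that should be settled before the data are open.

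The first is what the SCFA outcome is. The heading and the text disagree on the analytes, and the heading omits both propionate and the total. An analyst could report whichever analyte separated the groups as the primary result and still be within the wording of the plan.

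The second is how the two primaries combine. If success on either is enough, two chances at 0.05 raise the overall false-positive rate. If success on both is needed, the error rate is protected but the chance of success falls below that of each test alone. The plan quotes one α and one power without saying which case it is in, so a reader cannot tell what those figures apply to.

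**Working it through.** **Inputs from the documents:** three groups of 22 (N = 66), effect size 0.4, α = 0.05, power 80%, two primary outcomes, two analytes in the assay heading and four in the text.

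**Assumptions:** 0.4 is Cohen's f; the test behind N = 66 is a one-way F test; all 66 patients are analysed. The documents give no correlations, so ranges are shown.

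**1. The plan's own figure.** For the F test on 2 and N − 3 degrees of freedom, with noncentrality λ = N × f²:
- N = 63: λ = 63 × 0.16 = 10.08, power 0.798.
- N = 66: λ = 66 × 0.16 = 10.56, power 0.818.

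With equal groups, 66 is the smallest total that reaches 80%. The stated N is therefore reproduced, for one test of one outcome at an undivided 0.05.

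**2. Either primary counts (one SCFA variable plus GLP-1).** If the two are independent, the false-positive rate is 1 − (1 − 0.05)² = 1 − 0.9025 = 0.0975. By simulation with 22 per arm it is about 9.3% at correlation 0.5 and 7.9% at 0.8. Range: about 8% to 10%.

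**3. Both primaries required.** The overall error rate stays at or below 0.05. Joint power, with f = 0.4 and the same pattern of group means on both outcomes:
- independent: 0.818² = 0.669;
- correlation 0.5 (simulated): about 0.71;
- correlation 0.8 (simulated): about 0.75.

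Joint power cannot exceed the single-test 0.818, so it reaches 80% only if the two outcomes are almost perfectly correlated.

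**4. Separate claims.** Each outcome has its own 0.05 and 81.8%, provided the SCFA variable was fixed in advance. If the analyte is chosen after the data, the SCFA claim succeeds by chance whenever any candidate reaches p < 0.05. Simulated with no true effect, with total SCFA as a weighted sum of the acids (assumed weights 0.6, 0.2, 0.2):

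| Candidates | Acids uncorrelated | Acid correlation 0.9 |
|---|---|---|
| Two (heading) | 9.8% | 7.0% |
| Four (text) | 15.8% | 8.3% |

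Equal weights change the four-analyte figures little (16.3% and 8.5%). The upper ends need uncorrelated acids.

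**The case against.** The strongest reply is that SCFA and GLP-1 are two questions, each reported on its own, so no joint rule is needed. This stands in part. Under that reading 0.05 and 80% hold per outcome, and whether separate claims call for a joint rule is partly a matter of convention. But the plan does not state it, the Hypothesis section puts both outcomes in one sentence, and the reading still needs a single SCFA variable.

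A second reply is that the analyte lists only describe what the laboratory will measure. That is fair, and it rules out a stronger reading. A reader might infer five primary tests (four analytes plus GLP-1), which if independent would give 1 − 0.95⁵ = 22.6%. No section says that each analyte is a primary test, and total SCFA overlaps with its components, so that figure is not supported. The count of primaries used here is two.

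A reader might also infer that N = 66 is a mistake. It is not: it is correct for a single three-group test.

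Thirdly, the power figures are conditional. The 75% needs the same group pattern on both outcomes; with opposite patterns and the same f, joint power at correlation 0.8 is about 64%. The figures also assume no losses, although the plan keeps only patients above 80% attendance and states no dropout allowance. And they belong to the F test, which is inferred from its match to 66. They do not carry over to a direct comparison of the two exercise groups. The gap between that comparison and the sizing is a separate point.

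**Conclusion.** The concern holds in a limited form. The SCFA primary variable is undefined, and the plan does not say how the two primaries lead to a conclusion. Under either joint rule one of the stated figures fails:

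- either counts: about 8% to 10% false positives instead of 5% (correlation 0.8 to 0);
- both required: about 67% to 75% joint power instead of 80% (correlation 0 to 0.8, F test, f = 0.4, same group pattern, all 66 analysed).

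Under separate claims both figures hold per outcome, but only once one SCFA variable is fixed. Left open, the error rate for the SCFA claim is about 7% to 10% with two candidate analytes and 8% to 16% with four, depending on how strongly the acids are correlated.

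The text facts are certain. The sizes depend on correlations that the documents do not give. Nothing in the documents shows an intention to select an analyte after the fact; the point is that the wording would allow it.

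**What to change.** Before any outcome data are seen:

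1. Make the assay heading and the text under it list the same analytes.
2. Name one SCFA primary variable, for example total SCFA in µmol/g, and say whether it is the end-of-programme value or the change from baseline, since that choice is open too.
3. Test SCFA and GLP-1 in a stated fixed order, each at 0.05.
4. Make the other analytes secondary, reported as estimates with 95% confidence intervals.

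**Cost.** This is wording only: no new assays and no increase in N. The overall error rate stays at 0.05, and the first outcome keeps 81.8% on the plan's own calculation. The price is that the second outcome cannot be claimed if the first fails. Its chance of being claimed is the joint power, about 67% to 75% under the assumptions above.

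If the sponsor prefers separate claims, or requires both outcomes, the plan should say so and restate the 80% as a per-outcome figure or as the joint figure. A multiplicity rule does not replace step 2, because it does not correct for an analyte chosen after the data.
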